**A STUDY OF STEREOTACTIC BODY RADIATION THERAPY
IN PATIENTS WITH UNRESECTED CARCINOMA
OF THE PANCREAS OR AMPULLA**

Coordinating Center:
University of Chicago Medical Center

[figure not shown]
Principal Investigator:
[name].
Department of Radiation and Cellular Oncology
[name]
[name]
[contact]
[contact]
[contact]

Co-Investigators:
Department of Radiation and Cellular Oncology
[name].
[name].
[name].

Department of Medicine, Section of Hematology/Oncology
[name].
[name].
[name].
[name].

Department of Surgery
[name].
[name].

SCHEMA

Patient Population: (see section 3.0 for complete eligibility)

- Biopsy-proven unresected cancer of the pancreas or ampulla
- No prior complete surgical resection
- ECOG performance status ≤ 2
- No prior history of radiation therapy to the abdominal area
- Primary tumor size ≤ 7.5 cm in largest diameter
- No duodenal invasion
- Patients with metastatic disease may be included if local symptoms are present

Required Sample Size: upto 24 patients, with 1-2 patients accrued per month

Study Center: University of Chicago Medical Center, Pritzker School of Medicine

Concept and Rationale: Cancers involving the upper gastrointestinal tract often present at advanced stages, and as such, are associated with an overall survival that may be less than one year after diagnosis. Because these cancers may progress both locally and distantly, a standard of care for unresected, non-metastatic disease is to administer both Radiation Therapy (RT) and systemic chemotherapy. Typically, radiation therapy is given concurrently with radiosensitizing chemotherapy using conventional fraction sizes (1.8-2 Gy/fraction), requiring 5-6 weeks of treatment.

In recent years, the ability to more precisely target and treat disease with RT has sparked interest in delivering larger fraction sizes (e.g., > 8 Gy/fraction), thereby reducing treatment time, and perhaps improving biologic effect. For other sites such as the lung and liver, this form of therapy (known as Stereotactic Body Radiation Therapy) has achieved high rates of local control, with no appreciable increase in toxicity of treatment in the observed time of follow-up.

From a practical standpoint, if there existed an effective and safe means to achieve local control and contract the length of RT into two weeks, patients would be more likely to tolerate aggressive systemic therapy. Meanwhile, with a positive initial experience in the unresectable setting, SBRT could be studied in the preoperative setting (e.g., for resectable or borderline resectable patients).

Primary Objective: To assess the maximum tolerated dose of delivering three fractions of SBRT and identify the appropriate dose for unresected carcinoma of the pancreas or ampulla

Secondary Objectives: To define toxicities, the post-treatment pain score, and quality of life, the rate of post-treatment resectability, and local control (as measured by CT or MRI and defined as lack of progressive disease by RECIST criteria).

Study Design:

- Dose escalation schema: Patients will be enrolled in a 3+3 dose escalation schema including doses of 10 Gy, 12.5 Gy, and 15 Gy. Once the MTD is reached, patients will be treated in an expanded cohort.
- Radiation therapy: The primary tumor will be treated with stereotactic body radiation therapy in three fractions over 10 days. Fiducial markers will be placed prior to therapy, when possible, to assist with localization. Respiratory gating will be used to help address movement of the target due to respiratory motion. Constraints to surrounding critical structures (duodenum, liver, kidneys, and spinal cord) will be observed.
- Chemotherapy: No concurrent chemotherapy will be administered with the RT. Patients will be allowed to receive chemotherapy prior to RT, although this is not required. Post-RT chemotherapy will be at the discretion of the treating physicians.
- Surgery: ability to achieve resection will be documented by completeness of resection (complete microscopic, incomplete microscopic, or gross residual). Re-evaluation for resectability will be at the discretion of the treating physician and not be a requirement of the study.

Statistical Methods: A 3+3 dose escalation design will be used. The maximum tolerated dose will be exceeded if 2 or more patients out of 6 (or a third or more) experience a dose limiting toxicity (DLT) at that dose. The dose immediately below will be recommended for further study. DLTs are defined as any acute toxicity of Grade 4 nausea, Grade 4 skin toxicity, Grade 3+ liver toxicity (metabolic or ascites), or Grade 3+ enteritis. Severe late toxicities of interest (occurring beyond the 4 week period of evaluation and up to 12 months after RT) will include any Grade 3+ gastrointestinal toxicity (such as small bowel ulcer, stricture, perforation, bleed, liver damage, pancreatitis, or cholecystitis). If the rate of any severe late toxicity of interest exceeds 25% (i.e., 7 or more patients in the expanded cohort of 18 treated at the MTD), the study committee will suspend accrual and determine whether further dose modifications are needed; the protocol will be amended accordingly.

TABLE OF CONTENTS

SCHEMA	ii
1. OBJECTIVES	1
1.1. Primary Objectives	1
1.2. Secondary Objectives	1
2. BACKGROUND	1
2.1 Unresectable carcinoma of the pancreas	1
2.2 Rationale	1
3. PATIENT SELECTION	3
3.1 Eligibility Criteria	3
3.2 Exclusion Criteria	3
3.3 Inclusion of Women and Minorities	4
4. TREATMENT PLAN	4
4.1 Radiation Therapy dose escalation	4
4.2 Measuring Health Related Quality of Life	4
4.3 Definition of Dose-Limiting Toxicity	5
4.4 General Concomitant Medication and Supportive Care Guidelines	7
4.5 Duration of Therapy	7
4.6 Duration of Follow Up	8
4.7 Criteria for Removal from Study	8
5. RADIATION THERAPY GUIDELINES	8
5.1 Treatment related planning procedures	8
5.2 RT planning parameters	8
5.3 RT Treatment	10
6. ADVERSE EVENTS	10
7. STUDY CALENDAR	133
8. MEASUREMENT OF EFFECT	144
8.1 Antitumor Effect – Solid Tumors	144
9. STATISTICAL CONSIDERATIONS	155
9.1 Study Design/Endpoints	155
9.2 Sample Size/Accrual Rate	166
9.3 Analysis of Secondary Endpoints	166
10. CONFIDENTIALITY	166
10.1 Patient confidentiality issue	17
REFERENCES	18
APPENDIX A	20
APPENDIX B	21
APPENDIX C	22
APPENDIX D	23

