4.3 Definition of Dose-Limiting Toxicity

The evaluation period of acute toxicity will be defined by the period of 28 days following the first fraction of RT. Dose Limiting Toxicity (DLT) will be defined according to Common Toxicity Criteria version 3.0 (See Appendix B) and includes the following acute toxicities:

- Grade 4 nausea (life-threatening consequences)
- Grade 4 skin toxicity (necrosis or ulceration of full thickness dermis, spontaneous bleeding from involved site)
- Grade 3+ liver toxicity including symptomatic ascites requiring invasive procedure, or total bilirubin $>3 \times$ ULN, or AST $>5 \times$ ULN, or ALT $>5 \times$ ULN that persists until day 28, and is attributable to radiation therapy.
- Grade 3+ enteritis (abdominal pain, fever, change in bowel habits with ileus, peritoneal signs) that is attributable to radiation therapy.

Patients must have a minimum of 3 weeks of follow-up after RT start for patient data to contribute enough follow-up for consideration of dose-limiting toxicity. However, any DLT that occurs with shorter follow-up will count towards the dose escalation rules. In addition, any grade 5 toxicity (i.e., death) considered possibly, probably or likely related to RT will be considered a DLT.

Any late toxicity that occurs beyond the 4 week period of evaluation will be closely followed and documented as a toxicity of interest. Included are the following severe late toxicities of RT:

- Grade 3+ gastrointestinal ulcer, fistula, stricture, or perforation (symptomatic and severely altered GI function, IV fluids or TPN ≥ 24 hrs, intervention indicated)
- Grade 3+ gastrointestinal mucositis (confluent ulcerations or pseudomembranes, bleeding with minor trauma)
- Grade 3+ gastrointestinal bleed (transfusion, interventional radiology or endoscopic or operative intervention)
- Grade 3+ gastrointestinal necrosis (inability to aliment adequately by GI tract, interventional radiology, intervention indicated)
- Grade 3+ liver toxicity including symptomatic ascites requiring invasive procedure, or total bilirubin $>3 \times$ ULN, or AST $>5 \times$ ULN, or ALT $>5 \times$ ULN, or asterixis, that is attributable to radiation therapy.

- Grade 3+ enteritis (abdominal pain, fever, change in bowel habits with ileus, peritoneal signs) that is attributable to radiation therapy.
- Grade 3+ pancreatitis (interventional radiology or operative intervention indicated)

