- Grade 3+ cholecystitis (interventional radiology or operative intervention indicated)

These severe, late toxicities will be evaluated between 1 and 12 months of therapy. There is no minimum follow-up time after RT start required for patient data to contribute enough follow-up for toxicities of interest.

Enrollment of 12 additional toxicity-evaluable patients at the MTD will provide a cohort of 18 patients at the putative MTD. If six or fewer of the 18 patients experience a toxicity of interest during the evaluation period, the combination will be considered tolerable. If 7 or more patients experience a toxicity of interest, the study committee will suspend accrual and determine whether further dose modifications are needed; the protocol will be amended accordingly. If the true probability of DLT at the MTD is 50%, the combination will be identified as too toxic with probability 0.88. If the true probability of DLT at the MTD is 25%, the combination will be identified as having an acceptable toxicity profile with probability 0.86.

Management associated with the above adverse events is outlined in Section 7.

Dose escalation will proceed within each cohort according to the following scheme. Dose-limiting toxicity (DLT) is defined above.

Number of Patients with DLT at a Given Dose Level	Escalation Decision Rule
0 out of 3	Enter 3 patients at the next dose level
≥ 2	Dose escalation will be stopped. This dose level will be declared the maximally administered dose (highest dose administered). Three (3) additional patients will be entered at the next lowest dose level if only 3 patients were treated previously at that dose.
1 out of 3	Enter at least 3 more patients at this dose level. 
 • If 0 of these 3 patients experience DLT, proceed to the next dose level. • If 1 or more of this group suffer DLT, then dose escalation is stopped, and this dose is declared the maximally administered dose. Three (3) additional patients will be entered at the next lowest dose level if only 3 patients were treated previously at that dose.
≤ 1 out of 6 at highest dose level below the maximally administered dose	This is generally the recommended phase 2 dose. At least 6 patients must be entered at the recommended phase 2 dose.

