6. ADVERSE EVENTS

Adverse event (AE) monitoring and reporting will be performed.

- Radiation side effects are limited to the area involved in the treatment field. Acute and late toxicity related to radiation therapy may include fatigue, nausea and vomiting, skin erythema, subcutaneous fibrosis, esophagitis, pericarditis, diarrhea, myelitis, damage to the small bowel (including stricture or obstruction, bleed, fistula formation, or perforation), liver dysfunction, kidney damage, and radiation enteritis.
- Acute toxicity including Grade 4 nausea, Grade 4 skin toxicity, and Grade 3 liver toxicity will be referred to as dose limiting toxicities (DLT).
- Late toxicity including any Grade 3+ GI toxicity (small bowel damage including stricture or obstruction, bleed, fistula formation, or perforation; liver damage including ascites but not including abnormal lab values only; pancreatitis, cholecystitis) will be considered a toxicity of interest.
- All life-threatening Grade 4 and all fatal toxicities (Grade 5) must be reported immediately and evaluated.

- Acute toxicity: Acute side effects are considered as occurring \leq 28 days from the start of radiation therapy. They will be documented using the NCI Common Terminology Criteria for Adverse Events (CTCAE) version 3.0 (A copy can be downloaded from <http://ctep.info.nih.gov>). The relevant sections are included in the appendix.
- Late toxicity: Late side effects are considered as occurring $>$ 28 days from the start of radiation therapy through a 12 month total evaluation period. They will also be documented using the NCI Common Terminology Criteria for Adverse Events (CTCAE) version 3.0. The relevant sections are included in the appendix.
- University of Chicago Reporting Guidelines
 - If the reaction requires reporting, the Research Nurse or MD reports the adverse reaction to the Cancer Clinical Trials Office (CCTO) at [contact] by the end of the business day when he/she becomes aware of the event. Events occurring after business hours will be reported to the CCTO by 12 pm (noon) the next business day.
 - The following information is required when calling in the event:
 - Caller's Name and Telephone Number
 - Patient Initials
 - Patient Medical Record Number
 - IRB Protocol Number
 - PI of Study
 - Attending Physician
 - Date of Event
 - Description of Event (including grade of the event and attribution of the event and if the event required hospitalization)

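### The late-toxicity suspension rule is described as a rate above 25% but fires only at 7 of 18 (38.9%), so 5 or 6 events exceed the stated rate yet are called tolerable

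*Combined protocol and SAP*

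**What the plan says.** The Schema, under Statistical Methods, has the study committee suspend accrual on this condition: "the rate of any severe late toxicity of interest exceeds 25% (i.e., 7 or more patients in the expanded cohort of 18".

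Section 4.3 gives the rule as a count only. The denominator is explained as "Enrollment of 12 additional toxicity-evaluable patients at the MTD will provide a cohort of 18 patients at the putative MTD". Then: "If six or fewer of the 18 patients experience a toxicity of interest during the evaluation period, the combination will be considered tolerable", and "If 7 or more patients experience a toxicity of interest, the study committee will suspend accrual". The same paragraph gives two operating characteristics. A true rate of 50% is identified as too toxic with probability 0.88, and a true rate of 25% is identified as acceptable with probability 0.86.

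Section 9.2 adds no threshold. It sends the reader to Section 5.2 for the late-toxicity rule, but Section 5.2 covers radiotherapy planning and contains no such rule.

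Two sections define what counts as a late liver event. The late-toxicity list in Section 4.3 has "Grade 3+ liver toxicity including symptomatic ascites requiring invasive procedure, or total bilirubin" above three times the upper limit of normal, or AST or ALT above five times that limit, or asterixis, if attributable to radiotherapy. Section 6 describes the liver component as "liver damage including ascites but not including abnormal lab values only".

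**The concern.** The Schema presents a percentage and a count as the same thing, and they are not. If 5 or 6 of the 18 patients have a qualifying event, the observed rate is above 25%, yet the count has not been reached and Section 4.3 declares the treatment tolerable. The committee would then have opposite instructions for the same data. Choosing between them after the events are known would be a post hoc safety decision.

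This is the only numerical rule on late toxicity. It decides whether accrual is suspended and whether the dose put forward under the primary objective is called tolerable. A reader of the Schema alone would believe that accrual stops once more than a quarter of patients are affected.

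The conflict over liver laboratory values bears on the same count: one patient can count under Section 4.3 and not under Section 6, in a rule that turns on one or two events.

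**Working it through.** **Inputs.** n = 18 (Schema; Section 4.3). Percentage trigger: above 25% (Schema). Count trigger: 7 or more (Schema; Section 4.3). Stated probabilities: 0.88 at a true rate of 50% and 0.86 at 25% (Section 4.3).

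**Formula.** With X the number of patients with an event and p the true rate, P(X ≥ r) = Σ C(18,k) p^k (1−p)^(18−k), summed over k = r to 18.

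**Step 1: reproduce the plan's figures.** At p = 0.5, P(X ≤ 6) = (1 + 18 + 153 + 816 + 3,060 + 8,568 + 18,564) / 262,144 = 31,180 / 262,144 = 0.1189, so P(X ≥ 7) = 0.8811 (stated 0.88). At p = 0.25, P(X ≤ 6) = 0.8610 (stated 0.86). Both reproduce. Cut-offs of 5 and 6 with n = 18, and cut-offs of 3 to 9 with n = 12 or n = 24, were also tried; none gives both figures.

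**Step 2: convert the percentage to a count.** 0.25 × 18 = 4.5. The observed rates are 4/18 = 22.2%, 5/18 = 27.8%, 6/18 = 33.3% and 7/18 = 38.9%. The first count above 25% is therefore 5.

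**Step 3: compare the two rules.**

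| True rate | P(suspend), 7 or more | P(suspend), 5 or more | P(exactly 5 or 6) |
|---|---|---|---|
| 25% | 0.139 | 0.481 | 0.342 |
| 30% | 0.278 | 0.667 | 0.389 |
| 33.3% | 0.391 | 0.769 | 0.377 |
| 40% | 0.626 | 0.906 | 0.280 |
| 50% | 0.881 | 0.985 | 0.104 |

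The last column is the difference between the other two (for example 0.4813 − 0.1390 = 0.342) and is the chance that the two statements disagree. Under the 7-of-18 rule, P(called tolerable) is 1 − 0.278 = 0.72 at 30%, 0.61 at one third, 0.55 at 35% and 0.37 at 40%. A 5-of-18 rule would accept a 25% rate with probability 1 − 0.481 = 0.519, so a literal 25% trigger cannot have the stated 0.86.

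**Step 4: the liver events.** The documents do not say how many events would be laboratory-only. As an illustration, suppose that counting them adds 5, 10 or 15 percentage points to a 25% rate. P(7 or more) then moves from 0.14 to its value at 30%, 35% or 40%: 0.28, 0.45 or 0.63.

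**The case against.** The strongest reply is that the operative rule is clear. The Schema and Section 4.3 give the same count, the Schema explains its percentage by that count, no section mentions 5, and the stated probabilities fit 7 of 18 exactly. On this view the defect is a loose percentage in a synopsis. It stands that the count rule is not miscalculated. But the percentage is still in the Schema as the trigger, and at 5 or 6 events it contradicts the count.

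A second reply is that rate could mean the underlying rate, with 7 as the evidence threshold. Since P(X ≥ 7) at 25% is 0.139 and P(X ≥ 6) is 0.283, 7 is the smallest count that speaks against a true rate of 25% at about a one-sided 14% level. That is coherent, but the documents do not say it, and the wording would still need repair. At more usual levels 7 events do not show it: the one-sided exact lower bound at 7/18 is 19.9% (95%) or 23.1% (90%).

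Third, passing a true rate of one third with probability 0.61 follows from a design set around 25% and 50%. It is not an arithmetic error. That is fair. The figure is relevant because the Schema's wording suggests protection that the count does not give.

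Two narrower points also stand. Section 6 provides other safeguards: immediate reporting and evaluation of all life-threatening Grade 4 and fatal toxicities, and weekly safety review. And the liver-event conflict is a separate matter of definition, whose assumed 5 to 15 points are not anchored in the documents; the finding on the threshold does not depend on them.

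**Conclusion.** The concern holds. The Schema equates an observed rate above 25% with 7 of 18, whereas the first count above 25% is 5. The two statements give opposite decisions at 5 and 6 events, an outcome with probability 0.34 to 0.39 at true rates of 25% to one third. At a true rate of 25% the probability of suspension is 0.14 under one reading and 0.48 under the other. The likely source is that 25%, used in Section 4.3 as the true rate to be accepted, was carried into the Schema as an observed-rate trigger. The conflict between Sections 4.3 and 6 over laboratory-only liver events is also real and affects the same count.

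The probabilities assume 18 independent patients with a common event rate and complete ascertainment to 12 months. Section 4.3 requires no minimum follow-up for these events and Section 2.1 notes that many patients survive less than a year, so observed counts would tend to be lower and suspension less likely than shown. Section 4.3 also words its two probabilities in terms of DLT although the rule counts late toxicities; they are read here as applying to the rule beside which they stand.

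**What to change.** Reconcile the Schema and Section 4.3 to one trigger before late events are counted. There are two consistent versions; which threshold is clinically right is for the study team to decide.

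- **Keep the count.** Remove the percentage trigger from the Schema, write 7 or more of 18 (39%), and say that 25% is the true rate treated as acceptable in the operating characteristics. This is the smallest change and the only one that fits the stated 0.88 and 0.86. Add the probabilities of suspension at true rates of one third (0.39) and 40% (0.63), so that the range between 25% and 50% is visible.
- **Keep the observed-rate trigger.** Change the count to 5 of 18 in both places, and restate the operating characteristics as 0.985 (too toxic at 50%) and 0.52 (acceptable at 25%).

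In either case, use one list of qualifying liver events in Sections 4.3 and 6, word the probabilities in Section 4.3 in terms of late toxicities of interest, and correct the cross-reference in Section 9.2.

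The cost is a wording amendment, with no added patients or procedures. Under the first version the stated 0.88 and 0.86 do not change, but the added figures show less protection than the Schema now implies. Under the second, accrual would be suspended in about half of trials (0.48) even at a true rate of 25%.

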1. OBJECTIVES

1.1. Primary Objectives

The primary objective is to assess the Maximum Tolerated Dose (MTD) of delivering three fractions of Stereotactic Body Radiation Therapy (SBRT), and identify the appropriate dose for treatment of unresected carcinoma of the ampulla or pancreas.

1.2. Secondary Objectives

Secondary objectives include defining toxicities, effect on pain score, and quality of life, the rate of post-treatment resectability, and local control (as measured by CT or MRI and defined as lack of progressive disease by RECIST criteria).

2. BACKGROUND

2.1 Unresectable Carcinoma of the Pancreas

Cancers involving the upper gastrointestinal tract often present at advanced stages. While surgical resection offers some potential for long-term disease control, few patients present when disease can be addressed with a successful resection. As such, many patients with this disease have an overall survival that is less than one year after diagnosis. Because these cancers may progress both locally and distantly, and cause significant symptoms, patients are candidates to receive a combination of local Radiation Therapy (RT) and systemic chemotherapy. For patients with non-metastatic pancreatic cancer, data support the use of 5-Fluorouracil and RT as a means to favorably impact overall survival (Moertel, 1981). Typically, RT is given concurrently with radiosensitizing chemotherapy using conventional fraction sizes (1.8-2 Gy/fraction), over 5-6 weeks of treatment. Fewer data are available to support the use of RT for carcinoma of ampulla. However, it is known that these cancers are aggressive and have high rates of recurrence after surgical resection (Carter, 2008). In the unresectable setting, whether patients present with locally advanced or metastatic disease, lack of treatment may result in local symptoms including pain, gastrointestinal or biliary obstruction, bleeding, or perforation. For patients who are candidates to receive therapy, RT may be a useful adjunct to systemic chemotherapy to palliate patients of these symptoms (Boz, 2001).

